## 9 ADVERSE EVENTS

To comply with worldwide standards and guidelines on clinical investigation adverse event reporting, the Sponsor has adopted uniform and worldwide applicable standard definitions and reporting timelines to be used and adhered to by the investigators.

### 9.1 Definitions / Types of Events

#### 9.1.1 *Adverse Event*

An adverse event (AE) is any untoward medical occurrence, unintended disease or injury, or untoward clinical signs (including abnormal laboratory findings) in subjects, users or other persons, in the context of a clinical investigation, whether or not related to the investigational medical device.

This definition includes events related to the investigational medical device or comparator and/or the procedures involved. This definition includes events related to the procedures involved. For users or other persons, this definition is restricted to events related to the use of investigational medical devices or comparators.

An AE can therefore be any unfavorable and unintended sign (including an abnormal laboratory finding), symptom, or disease temporally associated with the use of a medicinal (investigational) product, whether or not related to the medicinal (investigational) product.

**Note:** Unchanged, chronic conditions are not adverse events and should not be recorded on the eCRF Adverse Event form. Pre-existing conditions that have not worsened are not considered AEs.

#### 9.1.2 *Serious Adverse Event*

Serious Adverse Event (SAE) is an AE that led to any of the following.

a) death,

b) a serious deterioration in the health of the subject, that resulted in any of the following:

- 1) life-threatening illness or injury
- 2) permanent impairment of a body structure or a body function
- 3) hospitalization or prolongation of patient hospitalization
- 4) medical or surgical intervention to prevent life threatening illness or injury or permanent impairment to a body structure or a body function
- 5) chronic disease

c) fetal distress, fetal death or a congenital physical or mental impairment or birth defect

**Note 1:** This includes device deficiencies that might have led to a serious adverse event if a) suitable action had not been taken or b) intervention had not been made or c) if circumstances had been less fortunate. These are handled under the SAE reporting system.

**Note 2:** A planned hospitalization for pre-existing condition, or a procedure required by the CIP, without a serious deterioration in health, is not considered to be a SAE. Such events will not count toward the primary endpoint.

### 9.1.3 *Anticipated Adverse Events*

**Table 4** summarizes the anticipated events that have been identified as possible complications from the Tendyne Transcatheter Mitral Valve System. Please also refer to the list of anticipated events in the Tendyne Transcatheter Mitral Valve System IFU and package insert for the Control device therapies required per protocol.

**Table 4. Anticipated Adverse Events (Tendyne Transcatheter Mitral Valve System)**

Adverse foreign body response	Foreign body response
Adverse reaction to anesthesia	Heart Failure, new or worsening
Allergic reaction	Hematoma
Anemia	Hemolysis
Annular dissection	Hypotension
Aortic insufficiency	Infection / sepsis
Atrial or ventricular injury	Leaflet, chordal, papillary or ventricular rupture (resulting from mitral valvuloplasty, if performed)
Atrial Septal Defect (resulting from mitral valvuloplasty, if performed)	Liver failure
Bioprosthetic valve dysfunction	Mitral valve injury
Bleeding complications	Mitral valve prolapse / stenosis
Blood loss which may require transfusion	Myocardial infarction
Cardiac arrest	Obstruction
Cardiac arrhythmia, Atrial or Ventricular	Pain
Cardiac perforation	Pleural effusion
Conduction defect, with or without need for pacemaker	Pulmonary embolism
Damage to cardiac tissue and/or structures	Pulmonary hypertension
Death	Paravalvular leak
Decreased LV function and/or cardiac output	Pericardial effusion / tamponade
Device embolism	Renal insufficiency or failure
Device erosion, migration or malposition	Respiratory difficulty, insufficiency or failure
Device thrombosis	Stroke or transient ischemic attack
Embolism (air, blood clot, calcium, tissue, etc.)	Tear or damage to device
Endocarditis	Vascular and access-related complications
Esophageal irritation, stricture, or perforation	Worsening of mitral regurgitation
Fever	

Normal postoperative sequelae or expected postoperative events during the acute perioperative period (72 hours) should not be recorded as SAEs unless they meet the seriousness criteria defined

in Section 9.1.2. A few common examples of normal post-operative sequelae or expected postoperative events include access-site pain, bruising, and events related to general anesthesia.

#### **9.1.4 Unanticipated Adverse Device Effect (UADE)**

Unanticipated Adverse Device Effect (UADE) refers to any serious adverse effect on health or safety or any life-threatening problem or death caused by, or associated with, the Tendyne Transcatheter Mitral Valve System, if that effect, problem, or death was not previously identified in nature, severity, or degree of incidence in the CIP, or application (including a supplementary plan or application), or any other unanticipated serious problem associated with a device that relates to the rights, safety, or welfare of subjects.

### **9.2 Device Deficiency**

Device deficiency (DD) is defined as any inadequacy in the identity, quality, durability, reliability, usability, safety or performance of an investigational device, including malfunction, use errors or inadequacy in the information supplied by the manufacturer including labeling.

**Note:** This definition includes device deficiencies related to the investigational medical device or the device comparator

**Note:** Cybersecurity incidents related to the investigational product, shall be reported as device deficiencies

A device malfunction is the failure of an investigational medical device to perform in accordance with its intended purpose when used in accordance with the instructions for use or CIP, or IB

### **9.3 Device / Procedure Relationship**

Determination of whether there is a reasonable possibility that the device, the implant procedure, or the patient condition (pre-existing condition) caused or contributed to an AE is to be **assessed by the investigator** and recorded on the appropriate eCRF. Additionally, the relationship to the device or procedure should also be categorized. This determination should be based on assessment of temporal relationships, evidence of alternative etiology and medical/biologic plausibility. Definitions for the determination of device- and/or procedure-relatedness include:

**Not Related:** Exposure to the device/procedure has not occurred (no temporal relationship), or the occurrence of the adverse event is not reasonably related in time, or there is a definite alternative etiology, or it is biologically implausible for the adverse event to be related to the use of the device.

**Possibly Related:** Exposure to the device/procedure has occurred; and it cannot be ruled out that the device/procedure is not responsible for the adverse event.

**Definitely Related:** Exposure to the device/procedure has occurred or the adverse event is related in time; and the device/procedure is definitely responsible for the adverse event.

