3.2 Adverse Events

All serious adverse device or procedure effects and UADEs will be summarized for all subjects who are randomized (ITT population of Randomized cohort) or underwent an attempted procedure (AP population for Non-repairable or Severe MAC Cohorts) in this trial in terms the number of events, the percentage of subjects with events. All CEC adjudicated adverse events will also be summarized similarly for all mITT, PP and AP populations. Moreover, COVID-19 related AEs will be summarized in terms of number of events, the percentage of subjects with events per MedDRA code.

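### Protocol 9.3 words Possibly Related with a reversed negation, so an exposed event that qualifies as Not Related also qualifies as Possibly Related, and no precedence is stated

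*Protocol*

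**What the plan says.** Protocol 9.3 opens with the standard to be applied: "Determination of whether there is a reasonable possibility that the device, the implant procedure, or the patient condition" caused or contributed to the event. The judgement is to be "assessed by the investigator", on the basis of timing, alternative causes and plausibility. Three categories follow.

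- **Not Related** applies when there was no exposure, when the timing does not fit, "or there is a definite alternative etiology, or it is biologically implausible for the adverse event to be related to the use of the device" (any one of these suffices).
- **Possibly Related** applies when exposure has occurred and "it cannot be ruled out that the device/procedure is not responsible for the adverse event".
- **Definitely Related** applies when "the device/procedure is definitely responsible for the adverse event", given exposure or a relation in time.

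No sentence says that the categories are exclusive or which one prevails if two are met. Protocol Appendix II carries a second causal scheme (device-, procedure- or patient condition-related). It has no intermediate level and no link to 9.3.

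On the analysis side, SAP 3.2 states that "All serious adverse device or procedure effects and UADEs will be summarized for all subjects who are randomized", with the Attempted Procedure population used in the single-arm cohorts. SAP VI.3.2 plans the same kind of summary for the Severe MAC CAP. SAP 3.2 adds that "All CEC adjudicated adverse events will also be summarized similarly for all mITT, PP and AP populations". MVARC Procedural Success (protocol Appendix II) requires the absence of major SAEs related to the device or procedure.

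**The concern.** The Possibly Related clause points the wrong way. The opening of 9.3 asks whether the device or procedure may have caused or contributed to the event; the clause asks whether it may *not* have done so. An event plainly due to something else satisfies that second question easily, because its non-responsibility certainly cannot be excluded. A rule meant to separate plausible from implausible attribution then admits both.

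At stake is the count of related serious events in the descriptive safety summaries, and one component of a descriptive composite. If sites resolve the wording differently, the same event could be counted as a device or procedure effect at one site and not at another.

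**Working it through.** No sample size, power or event count is involved, so the check is logical. Take an event by exposure and by what is known about causation, and apply the three definitions of 9.3. The check assumes that an exposed event meeting a Not Related criterion is one for which the device or procedure is judged not responsible.

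**As written**

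| Event | Not Related | Possibly Related | Definitely Related |
|---|---|---|---|
| No exposure | yes | no | no |
| Exposed, judged not responsible | yes | **yes** | no |
| Exposed, cause uncertain | no | yes | no |
| Exposed, certainly caused | no | no | yes |

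The second row is the defect. Take a pneumonia after implant with a definite alternative cause. The alternative cause makes it Not Related. Exposure has occurred and non-responsibility cannot be ruled out, so it is also Possibly Related. The third row is unaffected: a gastrointestinal bleed on anticoagulation, to which the device or procedure may have contributed, meets Possibly Related only.

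**With the *not* before *responsible* removed**

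| Event | Not Related | Possibly Related | Definitely Related |
|---|---|---|---|
| No exposure | yes | no | no |
| Exposed, judged not responsible | yes | no | no |
| Exposed, cause uncertain | no | yes | no |
| Exposed, certainly caused | no | **yes** | **yes** |

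The overlap between opposite categories disappears. What remains is ordinary nesting of Definitely within Possibly, which a precedence statement settles.

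**Where relatedness is used**

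- Protocol 9.4.1: relationship is recorded for each event, but all SAEs are collected whatever the category.
- Protocol 9.4.2 and Table 5: sites report every SAE within three calendar days, or sooner if local rules require, regardless of category.
- Protocol 9.1.4: UADEs have their own definition.
- Protocol 3.1 to 3.5: no primary or secondary endpoint uses relatedness to device or procedure.
- SAP 3.2 and VI.3.2, and MVARC Procedural Success: relatedness is needed to select events.

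**Bounds.** On a literal reading, the related count in those outputs could lie anywhere from definite plus uncertain events up to all post-exposure SAEs. On the intended reading nothing changes. The documents give no SAE counts, so the range cannot be narrowed.

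**The case against.** The strongest reply is that the meaning is clear from the section itself. The opening sentence sets a reasonable-possibility standard, and the Not Related criteria apply the same tests of timing, alternative cause and plausibility. The double classification arises only if one clause is read apart from its label and its preamble, and most investigators would probably classify correctly. This stands as a limit on the likely effect. It does not make the clause right: it is the operative definition, and it contradicts the standard it is meant to apply.

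A second reply is that independent adjudication stands behind the investigator. Protocol 12.11.5 gives the CEC adverse event adjudication, 12.7.4 sends it SAEs that require adjudication, and Appendix II has it judge relationship for primary and secondary endpoint events. This stands in part. Adjudication of relationship is stated only for endpoint events, so another SAE may carry the investigator's category alone. The CEC Charter and the case report forms are separate documents and may carry different wording.

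A reader might infer three stronger things that the documents do not support.

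- *That the 9.3 rule drives the ITT safety table.* SAP 3.2 selects on relatedness, but it does not cite 9.3 or say whether the investigator's or the CEC's call is tabulated.
- *That every post-exposure event short of Definitely Related falls in two categories.* Events of uncertain cause meet Possibly Related only.
- *That related counts would differ by arm.* The same wording applies to both arms. Site staff know the assignment, but nothing in the slip acts differently on one arm.

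**Conclusion.** The point holds as a wording error in an operative classification rule. Its reach is confined to exposed events that already meet a Not Related criterion, and its consequences to descriptive outputs: the serious device or procedure effect summaries in SAP 3.2 and VI.3.2, and MVARC Procedural Success. Inference on the primary and secondary endpoints is untouched. Because SAEs are captured regardless of category, relatedness could be re-reviewed without new data.

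The size is unknown and may be small or nil. It depends on two things the documents do not settle: how literally investigators apply the clause, and whose relatedness call is tabulated. The correction is still worth making, because the rule is wrong as written and the remedy is nearly free.

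**What to change.** In protocol 9.3:

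1. Delete the *not* before *responsible* in Possibly Related, so that the test is whether responsibility of the device or procedure cannot be ruled out.
2. State that each event is assigned to exactly one category: Not Related if any of its criteria is met; otherwise Definitely Related takes precedence over Possibly Related.
3. Check that the eCRF help text carries the corrected wording.

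The cost is a one-word deletion, one added sentence on precedence, the eCRF check and a short note to sites. No new data are needed.

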## **9.4 Adverse Event / Device Deficiency Reporting**

### ***9.4.1 AE Reporting***

The investigator will monitor the occurrence of adverse events for each subject during the course of the trial. Event description, date of onset, severity, duration, and relationship to device and/or procedure will be recorded on the appropriate eCRF by the investigator or designee.

For subjects implanted with the Tendyne valve, a TTE must be conducted if signs or symptoms suggestive of valve dysfunction are exhibited. If the TTE indicates evidence of valve dysfunction, a cardiac CT must be performed. If renal insufficiency precludes a cardiac CT, a TEE must be performed instead.

For this clinical investigation, only SAEs, regardless of device and/or procedural relatedness, will be collected on each subject from the time of trial registration through trial completion. A summary of AE reporting requirements is further described in this section and summarized in

#### **Table 5.**

Unchanged, chronic, non-worsening or pre-existing conditions are not AEs and should not be reported.

The Sponsor will provide an offline form to allow the investigator to report SAEs in the event entry cannot be made in the EDC. This does not replace the EDC reporting system and sites must still enter all information in the EDC system as soon as feasible.

### ***9.4.2 SAE Reporting to Sponsor and IRB / EC***

SAEs may be reported by the subject, observed by the investigator, or documented in medical records and must be reported to the Sponsor on the Adverse Event eCRF. Additional information related to previously reported SAEs should be updated within the eCRF as soon as the information has been reviewed and verified by the investigator.

The investigator should report all SAEs to the Sponsor as soon as possible but no later than three (3) calendar days from the day the trial personnel became aware of the event or as per the investigational site's local requirements, if the requirement is more stringent than those outlined.

The date the site staff became aware the event met the criteria of an SAE must be recorded in the source document. The investigator will further report the SAE to the local IRB/EC according to the institution's IRB/EC reporting requirements.

### ***9.4.3 UADE Reporting to Sponsor and IRB***

The Sponsor requires the investigator to report any UADE to the sponsor within three (3) calendar days of the investigator's knowledge of the event, unless local requirements are more stringent, and to the IRB/EC per requirements.

### ***9.4.4 Device Deficiency Reporting***

The investigator should report all device deficiencies related to the Tendyne device to the Sponsor as soon as possible but no later than three (3) calendar days from the day the trial personnel becomes aware of the event or as per the investigative site's local requirements if the requirement is more stringent than those outlined. Device deficiencies should also be reported to the IRB/EC per the investigative site's local requirements.

The device, if not successfully implanted in the subject, should be returned to the Sponsor. Device deficiencies/malfunctions should be reported to the IRB/EC per the investigative site's local requirements.

#### **9.4.5 *Investigational Site AE Reporting Requirements to Sponsor***

Investigators are responsible for preparation and submission to the Sponsor of all reportable AEs and DDs identified in the CIP. Adverse event reporting requirements are included in **Table 5**. All reports are subject to inspection and to the retention requirements described in **13.6.1 Investigator Records**.

**Table 5. Investigational Site AE Reporting Requirements to Sponsor**

Event	Investigational Site	Reporting timelines
SAE	All Sites	SAEs must be reported no later than three (3) calendar days from the day the trial personnel became aware of the event or as per the investigative site's local requirements, if the requirement is more stringent than those outlined.
UADE	All Sites	UADEs must be reported no later than three (3) calendar days from the day the trial personnel became aware of the event or as per the investigative site's local requirements, if the requirement is more stringent than those outlined.
Device Deficiency	All Sites	DDs must be reported no later than three (3) calendar days from the day the trial personnel became aware of the event or as per the investigative site's local requirements, if the requirement is more stringent than those outlined.

#### **9.4.6 *AE Reporting to Country Regulatory Authorities by the Sponsor***

The Sponsor will report SAEs, UADEs, and DDs to the country regulatory authority, per local requirements.

**Note:** Reportable device deficiencies include those that might have led to an SAE if a) suitable action had not been taken or b) intervention had not been made or c) if circumstances had been less fortunate. These are handled under the SAE reporting system.

#### **9.5 Heart Transplants or Subject Death (Tendyne Only)**

In the event of heart transplant or subject death, histological and engineering analyses of the *in situ* valve would provide valuable information. The Sponsor must be contacted for shipping and packaging materials and to arrange for transport.

### **10 STATISTICAL METHODS**

The following section describes the statistical methods for the clinical investigation. Additional details are provided in a Statistical Analysis Plan (SAP).

## 10.1 Analysis Populations

### 10.1.1 Randomized Cohort

The Intention-to-Treat, modified Intention-to-Treat and Per-Protocol are defined below. For all the analyses, the duration of follow-up will be calculated from the date of registration.

#### Intention-to-Treat (ITT) Population

[REDACTED]

#### Modified Intention-to-Treat (mITT) Population

[REDACTED]

#### Per-Protocol (PP) Population

[REDACTED]

### 10.1.2 Non-repairable, Severe MAC and Severe MAC CAP Cohorts

#### Attempted Procedure (AP) Population

The Attempted Procedure population for the Non-repairable and Severe MAC cohorts will consist of subjects in whom a Tendyne procedure is attempted.

[REDACTED]

## 10.2 Statistical Analyses

### 10.2.1 Randomized Cohort

#### Randomized Cohort – Primary Composite Endpoint

The primary endpoint for the Randomized cohort is freedom from all-cause mortality and heart failure hospitalization (HFH) at 12-months post index procedure. The trial is intended to demonstrate non-inferiority of the Tendyne Transcatheter Mitral Valve System to TEER with MitraClip for the treatment of moderate-to-severe or severe MR.

The null ( $H_0$ ) and alternative ( $H_1$ ) hypotheses are:

$$H_0: \pi_D - \pi_C \leq -d$$

[REDACTED]

[REDACTED]

$$\mathbf{H_1: \pi_D - \pi_C > -d}$$

where  $\pi_D$  and  $\pi_C$  are the true event rates for the composite of freedom from all-cause mortality and HFH at 12 months in the Treatment and Control group, respectively, and  $d$  is the non-inferiority margin. The non-inferiority margin is set at 12.5%.

The primary analysis for the primary endpoint will be performed on the ITT population. The analysis will also be performed on the mITT and PP populations.

one-sided test with 5% significance level.

### **Randomized Cohort – Secondary Endpoints**

The following secondary endpoints will be evaluated. These endpoints will be evaluated for labeling claims if the primary endpoint for the randomized cohort is met.

Effectiveness: Freedom from MR > mild in severity at 30 days post index procedure among survivors

Subjects treated with the Tendyne device are expected to experience greater reduction in MR severity than subjects in the Control group. The proportion of subjects with  $MR \leq \text{mild (1+)}$  at 30 days will be compared between the Treatment and Control groups.

The null and alternative hypotheses are stated as:

$$\mathbf{H_0: P_D - P_C \leq 0}$$

$$\mathbf{H_1: P_D - P_C > 0}$$

where  $P_D$  and  $P_C$  represent the proportion of subjects with  $MR \leq 1+$  at 30 days in the Treatment and Control groups, respectively. at one-sided 2.5% significance level. The primary analysis for this secondary endpoint will be performed on the ITT population.

Safety: Freedom from all-cause mortality and MV reintervention at 12 months

The Tendyne device may reduce the risk for surgical reintervention and subjects in the Treatment group are expected to experience greater reduction in MR severity than subjects in the Control group. The proportion of subjects alive and without MV reintervention at 12 months will be compared between the Treatment and Control groups.

The null and alternative hypotheses are stated as:

$$\mathbf{H_0: \pi_D - \pi_C \leq -d}$$

$$\mathbf{H_1: \pi_D - \pi_C > -d}$$

where  $\pi_D$  and  $\pi_C$  are the true event rates for the composite of freedom from all-cause mortality and MV reintervention or reoperation at 12 months in the Treatment and Control group, respectively, and  $d$  is the non-inferiority margin of 10%. [REDACTED]

[REDACTED]  
a one-sided test with 2.5% significance level. [REDACTED]

